- 4. Kirby delay discounting task and adapted delay and probability discounting task for food and money: to assess temporal impulsivity and risk aversion to money and food (Kirby K et al, Psychno Bull Rev 3:100-104, 1996, Kirby KN et al, Addiction. 99(4):461-71, 2004, Perry JL, & Carroll ME. Psychopharmacology 200:1-26, 2008, Weller RE et al. Appetite. 51:563-9, 2008, Davis C et al. Appetite. 54:208-13, 2010; de Ridder D et al. PLoS ONE, 9, e111081, 2014) (non-scan and scan visit).
- 5. Progressive ratio task to measure food reward in which subjects earn a sweet fatty candy (M&M Crispy; Mars UK Ltd) for their effort in clicking a computer mouse (*scan visit*). On subsequent trials the effort required to earn a candy is increased. The point at which they stop clicking to obtain a reward represents the break point, which is a measure of the reinforcer value ([name] et al. Am J Clin Nutr 96:467-73, 2012). The breakpoint for high-energy foods may be reduced after bariatric surgery.
- 6. Wechsler Test of Adult Reading (WTAR): to document intellectual and cognitive level (Green RE et al. J Clin Expt Neuropsychology 30:163-172, 2008) (at 1st scan visit only).

DNA sampling

Blood will be taken at the first scan visit, with specific consent, to extract DNA and RNA to enable examination of genetic variations in candidate genes associated with obesity, insulin resistance,

glucose metabolism, appetite regulation and reward, such as MC4R and FTO, e.g. using DNA sequencing and PCR based SNP analysis (Frayling et al. Science 316:889-94, 1007; Dina et al. Nat Genetics 39: 724-6, 2007; Chambers et al. Nat Genetics 40: 716-8, 2008; Loos et al Nat Genetics 40:768-75, 2008; Xiang et al. Biochemistry 45:7277-88, 2006). Such genetic variations have the potential to alter brain activation to food and non-food reward. DNA and RNA will be analysed through commercial genotyping of single nucleotide polymorphisms using pseudoanonymised samples. This is identical to several other studies of appetite and body composition by the Investigators which already have ethical approval (07/Q0406/19, 08/H0707/163, 08/H0707/139, 07/Q0411/19, 10/H0707/60, 14/LO/0871).

Food diaries

Prior to each scan scan visit participants will be asked to keep a food diary for 3 days using a written booklet or via an on-line record (www.myfood24.org/web/).

Bio-electrical impedance analysis

This painless, safe procedure involves standing upright on a metal platform while holding handles in each hand for up to 1 minute (Tanita).

Urine pregnancy tests

All participants will have a urinary pregnancy test at the 1st non-scan visit and at each scanning visit. If positive they will be excluded from the brain imaging study.

Stool sample

Participants will be supplied with a sealable stool collection container ('Fecotainer' - see supplemental page) at non-scan visits and asked to collect a stool sample either the day prior to or the morning of their scan visit and bring it along. This sample will undergo DNA analysis to identify the species and quantity of gut bacteria present, as well as changes in its chemical composition that may result. Recent studies have found that obesity and bariatric surgery procedures may alter the types and quantity of bacteria that are present in the bowel and the chemicals they produce, and that this itself may contribute to weight loss (Li JV et al. Gut 60:1214-23, 2011). Analysis of samples will be performed in collaboration with [name], Dept. of Surgery and Cancer, and [name], Dept. of Metabolism, Digestion and Reproduction, Imperial College London.

Serial blood sampling

Venous blood samples will be taken at intervals throughout the study mornings. No more than 200 mls will be taken on the non-scan visits and 150 mls on each of the scanning visits, totalling 700 mls over the duration of the study. Plasma levels of glucose and other metabolites, adipocytokines, insulin and other hormones (including ghrelin, GLP-1, PYY) will be measured by immunoassay.

Urine and blood metabonomics

Samples of urine, serum and plasma will be collected for analysis of its chemical composition by mass spectrometry and magnetic resonance spectroscopy (Li JV et al. Gut 60:1214-1223, 2011). This analysis provides information about metabolic changes in obesity and after surgery or dietary changes. This also complements the information obtained from analysis of stool sample bacteria and chemical composition, as different bacteria produce different metabolites that can be measured in urine. Analysis will be performed in collaboration with [name], Dept. of Metabolism, Digestion and Reproduction, Imperial College London.

Visual analogue scales

Visual analogue scales will be used to assess subjective feelings including hunger, nausea, fullness, sleepiness, stress, anxiety, volume of food that can be eaten and food palatability at intervals throughout the study visits (Questionnaire 27).

Magnetic resonance imaging

Participants will have a brain magnetic resonance (MR) scans for up to 90 mins on each scan visit. None of the MR techniques to be used employs ionizing radiation or intravenous contrast agents. Scanning will be performed on the 3.0 Tesla scanner in the Clinical Imaging Centre at the Hammersmith Hospital. Subjects lie supine in the scanner with their head placed in a padded head coil for support. While in the scanner volunteers will have access to a buzzer to sound an alarm, and will be able to hear and respond to instructions from the scanning console. While in the scanner subjects view a mirror reflecting a computer screen mounted above or behind the head coil. Subjects can respond to instructions using a keypad or joystick held in their hand. Subjects can rate their hunger and mood at various times while in the scanner using this device.

It should be noted that these scans cannot be viewed as a comprehensive health screening procedure. However, vary rarely, unexpected information can be detected which may warrant further investigation. In this event, a report will be sent to the volunteer's GP, who will arrange further tests and coordinate further care. Significant structural anatomical abnormalities may also preclude the subject from further participation in the study. The anatomical brain MR scans will be reported by a Consultant Neuroradiologist at Imperial College Healthcare NHS Trust or an equivalently qualified deputy.

The following anatomical brain scans will be collected at one or more of the visits:

(i) anatomical T1 and T2-weighted MR scans to provide structural data on which to overlay the functional data.

(ii) diffusion tensor imaging to examine white matter tracts.

The following resting state functional brain scans will be collected:

(iii) arterial spin labelling to measure resting regional blood flow (Petersen et al. Br J Radiol. 79:688-701, 2006; Paiva et al. NMR Biomed. 20(7):633-42, 2007). A radiofrequency (RF) pulse is applied to the neck so as to 'magnetically-label' blood in vessels that send blood to the brain. Subsequent MR scanning of the brain is therefore able to detect blood flow changes as the labelled blood circulates.

(iv) resting state BOLD functional MRI to measure regional connectivity in activity in different brain regions at rest (Damoiseaux JS et al. Proc Natl Acad Sci 103(37):13848-53, 2006).

The following task-related functional MRI scans will be collected at each visit:

(v) Food pictures: subjects view a variety of different pictures (e.g. food, household objects, animals, blurred pictures as a baseline) and rate how 'appealing' the pictures are using the keypad (Goldstone AP et al, Am J Clin Nutr 99:1319-30, 2014; Scholtz S et al. Gut 63:891-902, 2014; Goldstone AP et al. J Clin Endo Metab 101:599-609, 2016).

(vi) Stress images and emotion recognition tasks: subjects view mildly negatively distressing images and neutral images from the International Affective Picture System (IAPS, NIMH Center for the Study of Emotion and Attention, University of Florida, Gainesville, FL, USA) (e.g. war, accidents) or faces displaying different emotions (e.g. fearful or happy) (Glaysher MA et al. BMJ Open. 7:e018598, 2017; McGonigle J et al. J Psychopharmacol. 2017 Jan;31(1):3-16).

(vi) Stress images and emotion recognition tasks: subjects view mildly negatively distressing images and neutral images from the International Affective Picture System (IAPS, NIMH Center for the Study of Emotion and Attention, University of Florida, Gainesville, FL, USA) (e.g. war, accidents) or faces displaying different emotions (e.g. fearful or happy) (McGonigle J et al. J Psychopharmacol. 2017 Jan;31(1):3-16).

(vii) Monetary incentive delay (MID) task: a game in which subjects need to press a button during a specific time window when given a cue on the computer screen in order to win hypothetical monetary prizes of differing amounts to assess reward responsivity and ventral striatum function (Knutson B et al, J Neurosci 21(16):RC159, 2001, Knutson B et al, Neuroimage. 12(1):20-7, 2000; McGonigle J et al. J Psychopharmacol. 2017 Jan;31(1):3-16).

(viii) Go/NoGo Task: to assess impulsivity via effects on response inhibitory control mediated in the prefrontal cortex-striatum (Horn NR et al, Neuropsychologia. 41(14):1959-66, 2003. Yan P et al, Am J Drug Alcohol Abuse. 35(5):284-9, 2009, Chao HH et al, BMC Neurosci. 14;10:75, 2009, Li CS et al, Neuroscience. 155(4):1142-51, 2008, Perry JL, & Carroll ME. Psychopharmacology 200(1):1-26, 2008 ; McGonigle J et al. J Psychopharmacol. 2017 Jan;31(1):3-16). The task contrasts brain activation during responses to infrequent no go signals (e.g. 'do not press' button when viewing an infrequent red arrow) compared to an implicit go baseline (e.g. 'do press' button when viewing a frequent green arrow).

Some of these tasks will be practiced outside of the MRI scanner on scan visits to habituate the participants to the experimental procedures. Subjects will have continuous heart or breathing rate and pulse oximetry monitoring while in the MR scanner.

Fixed lunch meal

At lunch time at the *non-scan visits* participants will be given a small liquid meal (Fortisip Copmpact Vanilla, Nutricia (250 mL 600 kcal) to assess hormone and glucose changes in the blood after food intake.

Test lunch meal

At lunchtime at the *scan visits*, participants will be presented with a meal consisting of 4 different dishes (2 soups, yoghurt and ice cream), asked to rate their taste using a computer program (www.sipm.co.uk), and then eat until they feel comfortably full.

SAFETY AND PROTECTION OF VOLUNTEERS

During each visit, at least one experienced researcher will monitor the volunteers and subjects will be encouraged to report any unusual or unpleasant sensation to the investigator immediately. Any significant adverse effects will lead to withdrawal of the individual from the study.

Some individuals may find the confined space of the MR scanner intolerable because of claustrophobia. This is therefore an exclusion criterion for recruitment to the study and they will have an opportunity to get used to the procedure during the dummy visit.

If, however, subjects experience discomfort within the scanner despite the measures taken to ensure patient comfort, the patient may request immediate cessation of the procedure with withdrawal from the scanner by ringing the patient alarm bell. The MRI produces a "hammering noise" but subjects wear earplugs and headphones to prevent discomfort or damage to hearing.

INCIDENTAL FINDINGS

It should be noted that the MRI brain scan cannot be viewed as a comprehensive health screening procedure. However, vary rarely, unexpected information can be detected which may warrant further investigation. In this event, the participant will be informed and a report will be sent to their GP, who will arrange further tests and coordinate their further care. In the rare event that we find a significant abnormality on their structural brain scan on the first visit this may exclude them from continuing with the rest of the Brain Imaging sub-study protocol or main study protocol.

OUTCOME MEASURES

Primary outcomes

Change in brain blood-oxygen level dependent (BOLD signal) using functional MRI in response to: (i) viewing food versus non-food pictures,

- (ii) viewing unpleasant vs. control pictures,
- (iii anticipation and receipt of non-food monetary reward using functional MRI,

(iv) inhibition of motor actions.

Secondary outcomes

Slope and area under curve to food and money in delay and probability discounting tasks Breakpoint in Progressive ratio task

Reaction time, choice frequency, and rating of food liking and wanting of high-fat vs low fat and sweet vs. savoury foods in LFPQ task

Food and non-food monetary value in food valuation task

Premature responding rate in 4-choice serial reaction time task

Changes in resting brain activity measured by resting fMRI connectivity and arterial spin labelling

Food intake during test meals Food intake (total energy and macronutrient composition) recorded at home Appeal score of food pictures versus non-food pictures Hunger, appetite, food palatability, fullness scores in visual analogue scales Lunch taste pleasantness, liking, sweetness, creaminess scores Gut hormone, leptin, glucose, and insulin levels Polymorphisms in genes related to obesity, appetite and addiction

Dutch Eating Behaviour Questionnaire (DEBQ) – restraint, emotional and external influences scores

Behavioural Inhibition and Activation System (BIS / BAS) scales – BAS drive, BAS reward responsiveness, BAS fun seeking, BIS scores

Three Factor Eating Questionnaire (TFEQ) restraint, disinhibition and hunger scores

Eysenck Personality Questionnaire (EPQ-R) scores

Positive and Negative Affect Scores from PANAS

Beck Depression Inventory (BDI-II) score

Barratt Impulsivity Scale score

Binge Eating Scale score

DS-R score

Arts and Sigstad questionnaires

Hospital Anxiety and Depression Scale (HADS)

Power of Food Scale

Short-Form 36 Health Survey Questionnaire (SF36)

IWQoL - total energy expenditure

Pittsburgh Sleep Quality Index (PSQI) score

UPPS-P Questionnaire

Alcohol Use Disorders Identification Test (AUDIT)

Yale Food Addiction Scale score and diagnosis

WTAR intellectual level

PEMS Questionnaire score

DMQ-R Questionnaire score

Exploratory outcomes

Changes in gut microbiota Changes in faecal water, plasma and urinary metabolites from metabonomic studies

DATA HANDLING AND RECORD KEEPING

Personal contact details are required for communication with the subjects participating in the study. This information is held solely for communication between the researchers and participants. Details stored on university computers will be password protected and will only be accessed by the researchers involved in the study.

Information held on NHS computers is solely for the purpose of hospital booking and routine sample collection and analysis (e.g. for medical screening). This information is password protected in a similar manner to that of other hospital patients.

Subjects will be given a personal study code number which will be used throughout the study and in the analysis of data. Coded samples will be treated with confidentiality, similarly to patient samples, when undergoing analysis both in the department and in the hospital laboratory.

Self-reported food consumption data will be recorded using a validated on-line tool at home, called Food24 (www.myfood24.org/web). myfood24 was designed by the University of Leeds and Imperial College London, the software was developed by Rippleffect and is now supported by Calls9 Limited. The hosting is provided by Digital Ocean. Participants using myfood24 can only access their own diary information. They are invited to complete a food diary via an email containing a link that is unique to them. Researchers using myfood24 are only able to access projects created by themselves unless they have been granted access to specific projects by the system administrator. The myfood24 administrator account is strictly controlled and only used for the purpose of system administration and maintenance. Only Calls9 programming staff assigned to the development of myfood24 have access to the application and the hosting servers. Access to myfood24 is only in response to maintenance requirements. Digital Ocean technical support staff do not have access to the backend hypervisors where virtual servers reside nor direct access to the NAS/SAN storage systems where snapshots and backup images reside. Only select engineering teams have direct access to the backend hypervisors based on their role. More information can be found at: https://www.digitalocean.com/legal/data-security/.

Data analysis will take place in the Department of Brain Sciences, and Metabolism, Digestion and Reproduction, Imperial College London and be carried out by the researchers themselves. The data will be kept in a secure environment in these departments, under the authority of [name] and [name]. Data will be stored for 10 years after completion of the study. Only the researchers will have access.

GLM	Generalised linear model
CSR	Clinical study report
SAE	Serious Adverse Event
TEAE	Treatment emergent adverse event
AE	Adverse Event
SOC	System organs class
РТ	Preferred Term
CRF	Case Report Form

STUDY DESIGN

This is an open-label randomised-controlled clinical trial to investigate the safety and efficacy of obesity surgery vs medical care for women with polycystic ovary syndrome (PCOS), obesity and oligo- or amenorrhoea.

Patients will be randomised at a ratio of 1:1, stratified by body mass index (BMI) and trial site to:

- Medical care: a combination of lifestyle modification and pharmacotherapy or
- Obesity surgery: standard laparoscopic vertical sleeve gastrectomy (VSG).

Key Inclusion criteria

- Pre-menopausal women ≥ 18 years old
- BMI \ge 35 kg/m² with obesity-related complications
- Diagnosis of PCOS based on international evidence-based guidelines for the assessment and management of PCOS 2018

Key Exclusion criteria

- Type 1 or Type 2 diabetes mellitus
- Specific contraindications to obesity surgery
- Previous obesity surgery
- Inability to maintain adequate contraception
- Medications affecting reproductive function (e.g. oral steroids, hormonal contraceptives) at screening or 3 months previously.
- Other causes of anovulation (e.g. untreated hypothyroidism, adrenal or pituitary disorders)
- Current pregnancy or breastfeeding

Key outcomes

Reproductive

- Weekly serum progesterone
- Monthly profile of reproductive hormones
- Self-reported menses

Metabolic

- Oral glucose tolerance test measuring glucose and insulin secretion and sensitivity indices. This will take place pre-intervention, at 26 weeks and 52 weeks post-intervention.
- Monthly metabolic profile: fasting glucose, insulin, and HOMA-IR.

2.1 INTERIM ANALYSIS

There will be no interim analysis for this study.

2.2 FINAL ANALYSES AND REPORTING

2.2.1 FINAL ANALYSIS

Our study will involve collecting data from all participants for 52 weeks. Once this follow-up period is complete, the database will be locked, and no further modifications will be made to it. The final analysis of the primary and secondary outcomes, as outlined in the protocol and this statistical analysis plan (SAP), will only be performed using the locked database. In addition to presenting results at the main

time point of interest (52 weeks), findings will also be presented at the 26-week mark, along with the baseline measurements.

2. STUDY OBJECTIVES AND ENDPOINTS

3.1 Study Objective

To perform an randomised controlled trial (RCT) comparing the safety and efficacy of obesity surgery vs medical care for women with PCOS, obesity and oligo or amenorrhea.

3.2 Study Endpoints

3.2.1 PRIMARY EFFICACY ENDPOINT

Primary efficacy outcome:

Number of ovulatory cycles within the 52-week follow-up period. Ovulation will be defined as a rise in serum progesterone ≥ 16 nmol/L.

3.2.2 SECONDARY EFFICACY ENDPOINTS

For each secondary endpoint, temporal changes, mean levels and peak levels will be analysed as appropriate:

- Anthropometric measurements body composition, waist circumference, body weight
- Metabolic outcomes glycated plasma haemoglobin (HbA1c), plasma liver function tests, plasma lipid profile
- Arterial blood pressure
- Reproductive hormones serum luteinising hormone (LH), follicle-stimulating hormone (FSH), oestradiol, sex hormone binding globulin (SHBG), testosterone, free androgen index (FAI), dehydroepiandrosterone sulfate (DHEAS), androstenedione, Anti Mullerian hormone (AMH)
- Number of reported menses
- Glucose concentrations at the oral glucose tolerance test (OGTT)
- Hospital Anxiety and Depression Scale (HADS) score
- Multidimensional Health Profile: Health Functioning questionnaire score
- PCOS Health-Related Quality of Life score
- Modified Ferriam-Galwey hirsutism score
- Ludwig visual score
- Savin alopecia scale score
- Cardiff Acne Disability index
- Number of medications

4 Sample Size

Based on the available data on the effect size of lifestyle interventions[1] and obesity surgery[2] on ovulation we estimated that women in the standard medical care group will have a mean of 7 and women in the obesity surgery group a mean of 10 ovulatory cycles in the 52-week follow-up period. With a standard deviation of 3.3 around both means, we will need 33 women in each group to have a 95% power to detect statistically significant differences between the groups at α of 0.05. We will recruit 40 patients in each group to account for a 15-20% drop-out rate based on rates in similar trials we have conducted in this field (LIPOS UTN: U1111-1126-3292 and DOMINO ISRCTN76278694).

5 ANALYSIS POPULATIONS

5.1 INTENTION TO TREAT POPULATION (ITT)

We will recruit 80 women, with each group comprising forty participants randomised at a 1:1 ratio. The intention-to-treat (ITT) population will include all patients who were initially assigned to either medical care or obesity surgery, regardless of any deviations from the trial protocol or the actual treatment they received. The analysis of this population will be based on their original assignment group.

5.2 PER-PROTOCOL POPULATION (PP)

The Per-Protocol (PP) analysis population includes the patients who completed their trial follow up at 52 weeks with no major deviations to the treatment protocol.

5.3 SAFETY POPULATION

We expect the rate of crossovers in our study to be low. We will analyse the safety population using the "as-treated" approach, which means that participants will be categorised based on the treatment groups they actually received. The safety population will comprise all randomised participants who underwent obesity surgery or medical care, and had at least one outcome measurement or clinical visit after randomisation.

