8.2 CONSENT

Consent to enter the study must be sought from each participant only after a full explanation has been given, an information leaflet offered and a minimum of 24hrs allowed for consideration. Signed participant consent should be obtained. The right of the participant to refuse to participate without giving reasons must be respected. After the participant has entered the study the clinician remains free to give alternative treatment to that specified in the protocol at any stage if he/she feels it is in the participant's best interest, but the reasons for doing so should be recorded. In these cases the participants remain within the study for the purposes of follow-up and data analysis. All participants are free to withdraw at any time from the protocol treatment without giving reasons and without prejudicing further treatment.

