9 SAFETY ANALYSES

9.1 PRIMARY SAFETY OUTCOME

The primary safety outcome will be the incidence risk of treatment-emergent serious adverse events (SAEs) through the 52-week follow-up period. We will evaluate this outcome via a Fisher's exact test. Results will be presented as numbers of patients with the event (percentage).

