9.3.1 ALL ADVERSE EVENTS

The total number of TEAEs and the number and percentage of subjects with at least one TEAE will be presented by treatment groups. A TEAE is an event starting or worsening in severity at or after initiation of the index procedure for the randomised treatment. For subject counts, subjects experiencing a given event more than once will be counted only once for that event.

A listing of all adverse events will include the subject number, adverse event (AE) number, the investigator description of the AE, the AE system organs class (SOC) and preferred term (PT), the severity of AE, whether or not the AE is classified as serious (SAE), the relationship of the AE to the procedure, the action taken, the outcome, and the adjudication status.

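### Safety is compared only by treatment received and only from an incompletely defined index procedure, so some harms in women assigned to surgery never count in that arm and no comparison by assigned arm is planned

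*SAP*

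**What the plan says.** SAP 5.3 sets two entry conditions and a grouping rule. Treatment condition: "The safety population will comprise all randomised participants who underwent obesity surgery or medical care". Contact condition: they must also have "had at least one outcome measurement or clinical visit after randomisation". Grouping: "participants will be categorised based on the treatment groups they actually received". It justifies the approach with an expectation, "We expect the rate of crossovers in our study to be low", and gives no figure.

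SAP 9.3.1 sets the clock: "A TEAE is an event starting or worsening in severity at or after initiation of the index procedure for the randomised treatment". SAP 9.1 makes the primary safety outcome the incidence risk of "treatment-emergent serious adverse events (SAEs) through the 52-week follow-up period" and adds "We will evaluate this outcome via a Fisher's exact test". The primary safety comparison therefore carries both the as-treated grouping and the index-procedure start.

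Elsewhere, SAP 5.1 defines an intention-to-treat (ITT) population by original assignment, but no safety comparison uses it. Protocol section 7 adopts the intention-to-treat principle and states no exception for safety. Protocol 8.2 says that "the clinician remains free to give alternative treatment to that specified in the protocol at any stage", and keeps such women in follow-up and analysis.

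**The concern.** The stated objective is a randomised comparison of safety as well as efficacy. Under these rules, membership of a safety group, and whether an event counts, depend on what happens after randomisation. That includes the events being compared: a woman who has a serious event or becomes unfit while waiting may for that reason not be operated on. She then leaves the surgical group together with her event.

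SAP 5.3 and 9.3.1 also pull apart. One sorts women by treatment received; the other times events by the randomised treatment. For a woman whose two treatments differ, the SAP does not say which clock applies or to which group her event belongs. At 40 per arm, a handful of such women can move the percentages by a point or more.

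**Working it through.** **No plan figure to reproduce.** The documents give no expected SAE rate, crossover rate or safety power. The sample size (33 per group, raised to 40) concerns ovulatory cycles. Only the 40 per arm is used here; every event count below is assumed.

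**Step 1. Apply the rules to each kind of woman.**

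| Woman | Group under SAP 5.3 | Treatment-emergent under SAP 9.3.1? | Effect on surgical arm |
|---|---|---|---|
| Assigned surgery, not operated on, regarded as having had medical care | Medical care | No, read literally: the procedure for her randomised treatment never began | Woman and event both absent |
| Assigned surgery, received neither treatment | Outside the population | No | Woman and event both absent |
| Assigned surgery, SAE before the operation, later operated on | Surgery | No, unless it worsens at or after the operation | Woman counted, event not |
| Assigned medical care, operated on during the year | No rule for a woman who had both | Timed from a start of medical care that is not defined | Undetermined |

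The first two rows are hard to tell apart. Protocol section 6 gives both arms multidisciplinary care, so it is unclear when an unoperated woman has received medical care.

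**Step 2. Direction for unoperated women.** Let *k* of the 40 assigned to surgery be unoperated, with *b* SAEs among them and *a* among the 40 − *k* operated on. The surgical percentage changes from (*a* + *b*)/40 to *a*/(40 − *k*). It falls when *b*/*k* exceeds *a*/(40 − *k*) and rises when it is below. If the women are moved rather than dropped, the medical-care denominator also grows, from 40 to 40 + *k*.

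**Step 3. Illustration, equal safety.** Assume 4/40 v 4/40 by assigned arm (difference 0) and *k* = 3.

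| SAEs among the three | Handling | Surgery | Medical care | Difference |
|---|---|---|---|---|
| 0 | Dropped | 4/37 = 10.8% | 4/40 = 10.0% | +0.8 |
| 0 | Moved | 4/37 = 10.8% | 4/43 = 9.3% | +1.5 |
| 1 | Dropped | 3/37 = 8.1% | 4/40 = 10.0% | −1.9 |
| 1 | Moved, event not counted | 3/37 = 8.1% | 4/43 = 9.3% | −1.2 |

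Fisher's exact p is 1.0 in every row. Counting the moved event under medical care would give 3/37 v 5/43 = 11.6%, a difference of −3.5 (p = 0.72), but that departs from the literal wording of SAP 9.3.1.

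**Step 4. Illustration, more SAEs with surgery.** Assume four unoperated women, with SAEs in 6 operated women, 2 unoperated women and 1 medical-care woman.

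- By assigned arm: 8/40 (20.0%) v 1/40 (2.5%), difference 17.5 points, p = 0.029.
- Unoperated women dropped: 6/36 (16.7%) v 1/40 (2.5%), 14.2 points, p = 0.048.
- Moved, events not counted: 6/36 (16.7%) v 1/44 (2.3%), 14.4 points, p = 0.042.
- Moved, events counted under medical care: 6/36 (16.7%) v 3/44 (6.8%), 9.8 points, p = 0.286.

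The literal wording shrinks the difference by about 3 points. The looser reading roughly halves it and takes it across 0.05. This example assumes a steep SAE rate (2 of 4) in unoperated women.

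**Step 5. Pre-operative events in women later operated on.** Here the denominator stays and only the numerator falls. If one of four surgical-arm SAEs came before the operation, 4/40 (10.0%) becomes 3/40 (7.5%). Whether medical care loses comparable early events depends on its undefined start.

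**The case against.** As-treated safety analysis is a common, prespecified choice, and it suits harms caused by an operation. The sponsor expects few crossovers. The events do not vanish: SAP 9.3.1 lists all adverse events, SAP 9.3.4 lists deaths, SAP 6.2 tabulates ITT discontinuations by reason, and SAP 9.3 counts withdrawals from any cause. All of this stands. But listings and a discontinuation table are not a between-arm comparison of SAEs, and the crossover expectation has no number behind it.

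Four stronger readings are tempting, and the documents do not support them.

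- **That the rules must favour surgery.** They remove women from the denominator as well as events from the numerator. If the unoperated women have no SAEs, the shift is against surgery.
- **That a woman with a serious event and no later visit is excluded.** SAP 5.3 asks for any one outcome measurement or clinic visit after randomisation, not one after the event. Progesterone is sampled weekly during follow-up, so few women should fail this.
- **That medical-arm women will commonly cross to surgery.** Protocol 8.2 permits alternative treatment, but protocol section 6 makes these women eligible for surgery after the trial and describes their group as not having it for 12 months.
- **That the treatment-emergent rule cannot work for medical care.** SAP 9.3.1 refers to the randomised treatment, and protocol section 6 lists both arms as interventions. The start of medical care is undefined, which a definition would cure.

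**Conclusion.** The concern holds in a limited form. As written, the primary safety comparison leaves out of the surgical arm any SAE in a woman assigned to surgery but not operated on, and any pre-operative SAE that does not worsen. No analysis by assigned arm shows what this does. Neither the direction nor the size of the bias can be settled from the documents. In the equal-safety example the shift is at most 1.9 points either way on the literal wording, with no change in the test result. Larger shifts need both a high SAE rate in unoperated women and the looser reading that counts their events under medical care. That two readings are possible is itself a reason to settle the wording before database lock. This is a worthwhile, low-cost improvement; it does not show that the safety analysis is invalid or that as-treated grouping should be abandoned.

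**What to change.** - In SAP 5.3 and 9.1, add a between-arm comparison of SAEs in all randomised women by assigned arm, with no treatment-received or contact condition.
- Count from randomisation to the same fixed time point in both arms. The end matters as much as the start: protocol section 6 runs follow-up for 12 months after the intervention, so without a common end any wait for surgery would lengthen the surgical window. Women never operated on need SAE ascertainment to that same date.
- Keep the as-treated analysis alongside it for procedure-related harm.
- In SAP 9.3.1, define the start of medical care and say what applies to a woman who never has her assigned procedure.
- For a crossover woman, assign each event in the as-treated table to the treatment she had received when it began, and reconcile SAP 5.3 with 9.3.1 accordingly.

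The cost is SAP wording and one extra table. Events before surgery dilute the procedure-specific picture in the new table, but the as-treated table still shows it. The sponsor must confirm that SAEs between randomisation and surgery are captured: protocol section 5.2 calls for all adverse events to be reported, but the schedule in Appendix 1 goes from baseline to monthly visits and shows no separate contact for that interval.
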